Study protocol

Observation of clinical effects of oxygen: nitrogen 50%:50% gas mixture application for minor invasive procedures in pediatric patients

Correspondence

[name] PhD

Department of Anesthesiology

Institute for mother and child health care,

[name]

[name],

Serbia

Email: [contact]

Date

30.09.2024.

Summary

Rationale

Reducing pain and anxiety, avoiding psychological trauma associated with medical procedures are the focus of pediatric anesthesiologist in everyday practice. Nitrous oxide is a useful option for children who require procedural sedation. It is easy to apply, has satisfactory sedative and analgetic effects. Side effects are transient and vanish after discontinuation. It has been used for decades in pediatric emergency department as well for procedural sedation and analgesia.

Objective

The aim of this study is to evaluate the analgetic and anxiolytic profile of oxygen: nitrogen 50%:50% gas mixture for minor invasive procedures in pediatric patients.

Study design

Single center prospective observational cohort study.

Study population

Patients from 1 to 16 years of age admitted to department of anesthesiology and intensive care therapy, Institute for mother and child health care. Inclusion criteria: age 1-16 years; patients scheduled for following procedures : venepunction, arterial line placement, nasogastric tube placement, urinary catheter placement, removal of thoracic drain, skin suture. Exclusion criteria, presence one of the following conditions: age <1 year or > 16 years; pneumothorax; pneumoperitoneum; pneumocephalus; otitis media; obstructive lung disease; upper airway infection; methylenetetrahydrofolate reductase (MTHF) deficiency; vitamin B12 deficiency; megaloblastic anemia; folate deficiency (Vitamin B9 deficiency); bleomycin sulphate therapy; neuropathy, pregnancy.

Main study endpoints

Primary endpoint is evaluation of pain intensity following the implemented procedure.

Secondary endpoints are evaluation of anxiolytic effect, achieved level of sedation and observation of possible side effects such as hypotension, bradycardia and desaturation.

Nature and extent of the burden and risks associated with participation, benefit and group relatedness

The risks of prospective collection of demographic data, pain and anxiety scores during and after gas mixture application are negligible and the burden is minimal.

1. INTRODUCTION

Separation of parents, anticipation of unknown procedure and pain related to it create fear and anxiety in children of all ages. Half of admitted children cry, fight with medical staff and panic when preparing for unpleasant procedures like venipunctures, bladder catheterizations, lumbar punctures, bone marrow aspirations, nasogastric tube placement, laceration repairs, and others. One of the most difficult challenges professionally and emotionally is learning to handle pain and stress related emotions in pediatric patients. Pain is defined by the International Association of the Study of Pain as “an unpleasant sensory and emotional experience associated with, or resembling that associated with, actual or potential tissue damage.” Expanded definition includes items that provide further context to the complex topic of pain: (1) pain is always a personal experience; (2) pain is different from nociception; (3) pain is learned through life experiences; (4) a person’s report of pain should be respected; (5) pain can have adverse effects on function and well-being; and (6) verbal description is one of several behaviors used to express pain.¹ Pain and its’ psychological components in children are often under-recognized and undertreated. Children with serious medical conditions as well as healthy children have to undergo significant amounts of painful medical procedures throughout childhood (e.g. vaccinations, venipuncture, heel lance, insertion of a peripheral venous catheter, bone marrow aspirations, lumbar punctures, etc). In the vast majority of infants, no analgesic strategies are employed.² Research has shown that exposure to pain and stress related to it early in life has long-lasting consequences in terms of increases in the risk for developing problems in adulthood (chronic pain, anxiety and depressive disorders). Therefore, adequate management of infant and child pain is imperative.^{3,4}

Reducing pain and anxiety, avoiding psychological trauma associated with medical procedures are the focus of pediatric anesthesiologist in everyday practice. Nitrous oxide (N₂O) is an effective sedative and analgetic agent for mildly to moderately painful pediatric procedures, particularly for short ones.^{5,6} It has been used for decades in Europe and USA for pediatric procedural sedation and analgesia (PSA) without serious adverse effects. European Society of Anesthesiology Task Force on Nitrous Oxide issued in 2019. a narrative review concerning use of N₂O procedural sedation and analgesia (PSA). This review states that N₂O can be efficiently and safely used for procedural sedation in pediatric population for a variety of procedures of light to moderate pain intensity.⁷

2. OBJECTIVES & HYPOTHESES

2.1. Objectives

The aims of this study are:

- to evaluate the efficacy of oxygen: nitrogen 50%:50% gas mixture in achieving analgesia in pediatric patients requiring minor invasive procedures
- to evaluate the efficacy of oxygen: nitrogen 50%:50% gas mixture in achieving desired sedation in pediatric patients requiring minor invasive procedures
- to evaluate safety profile of oxygen : nitrogen 50%:50% gas mixture in achieving desired sedation in pediatric patients requiring minor invasive procedures

Minor invasive procedure investigated in this study are venepunction, arterial line placement, nasogastric tube placement, urinary catheter placement, removal of thoracic drain and kin suture

2.2. Hypotheses

- application of oxygen: nitrogen 50%:50% gas mixture will achieve pain relief in pediatric patients requiring minor invasive procedures
- application of oxygen: nitrogen 50%:50% gas mixture will achieve anxiolysis in pediatric patients requiring minor invasive procedures

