4.4. Sample size calculation

Based on previous published data estimated number of patients required to evaluate analgetic and anxiolytic effect as well as safety profile is between 32 and 90.^{8,9,10} We aim to observe 300 occasions that required oxygen: nitrogen 50%:50% gas mixture in order to draw unbiased conclusions.

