6. PROTOCOL

Application of gas mixture will be conducted via suitable face mask, flow calculated to achieve ventilation minute volume (MV) in accordance to age, $MV \text{ (L/min)} = \text{tidal volume (Vt)} \times \text{respiratory rate (RR)}$.

6.1 Management of side effects:

- 1 desaturation – supplemental oxygen via face mask
- 2 hypotension – iv fluids, vasoactive drugs if needed
- 3 bradycardia – atropine 0,2 mg iv

Important note – side effects such as hypotension, bradycardia are not expected to occur regarding good pharmacodynamic profile of nitrous oxide on cardiovascular system. However, implementing and monitoring these possible effects during the study increases the safety profile of the study

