7. STATISTICS

Descriptive statistics will be used to describe baseline characteristics. Categorical variables will be expressed as n (%), continuous variables as median [IQR]. Depending on data distribution parametric or nonparametric test will be used to explain relationship regarding outcome variables.

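### Sections 2.1 and 2.2 claim efficacy, but a single cohort without a comparator can only describe outcomes under the gas, and anxiolysis has no stated pre-gas reading

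*Protocol*

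**What the plan says.** The protocol states its aim at two strengths. The Summary's objective is "to evaluate the analgetic and anxiolytic profile of oxygen: nitrogen 50%:50% gas mixture for minor invasive procedures". Section 2.1 goes further: "to evaluate the efficacy of oxygen: nitrogen 50%:50% gas mixture in achieving analgesia", with a parallel bullet for sedation. Section 2.2 then makes two predictions: that "application of oxygen: nitrogen 50%:50% gas mixture will achieve pain relief in pediatric patients requiring minor invasive procedures", and that the gas "will achieve anxiolysis in pediatric patients requiring minor invasive procedures".

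The Summary calls the design a "Single center prospective observational cohort study". Section 4.4 sets the target: "We aim to observe 300 occasions that required oxygen: nitrogen 50%:50% gas mixture". Section 6 describes only how the gas is given ("Application of gas mixture will be conducted via suitable face mask"). No section names a control group, a historical rate or a success threshold for the cohort. Section 7 offers descriptive statistics and says that a "parametric or nonparametric test will be used to explain relationship regarding outcome variables".

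Section 5.1.2 defines the anxiolytic effect as the child's cooperability, in two states: carries out orders or refuses them. It gives no time point for this item. Heart rate, blood pressure and oxygen saturation are the only variables with a stated reading before the gas. The only timing given for anxiety scores is in the Summary's paragraph on burden and risk, which places them during and after the gas.

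**The concern.** Efficacy and relief are comparative ideas: they need an outcome without the gas, or a justified reference value. This design supplies neither. A high share of occasions with little pain or good cooperation would fit an effective gas, but it would also fit children and procedures that would have gone well anyway. The Summary's wording matches what the design can deliver; sections 2.1 and 2.2 do not.

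The anxiolysis endpoint has a further problem. It records a state and labels it an effect. Followed as written, a child who was already cooperative before the mask counts as anxiolysis achieved. The reported percentage then mixes children who became cooperative with children who simply stayed so, in unknown shares. If the observation is not made at the bedside, no later analysis plan can recover it.

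**Working it through.** **1. The plan's own figures.** Section 4.4 gives 32 to 90 patients from published studies and a target of 300 occasions. It states no significance level, power, effect size or event rate, so these figures can be neither reproduced nor refuted. The point here does not depend on them.

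**2. A larger sample does not replace a reference rate.** Take n = 300 and an assumed rate p0 of good outcome without the gas. Find the smallest count r with P(X ≥ r | 300, p0) ≤ 0.025 (exact binomial, one-sided).

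| Assumed rate without gas | Occasions needed to exceed it |
|---|---|
| 0.5 | 168 (56.0%) |
| 0.6 | 198 (66.0%) |
| 0.7 | 226 (75.3%) |
| 0.8 | 254 (84.7%) |

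A result of 240/300 = 80% would exceed a no-gas rate of 0.5, 0.6 or 0.7, but not one of 0.8. The protocol gives no such rate, so the same result could support the hypothesis or fail to.

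**3. Anxiolysis when nothing changes.** Let p be the share cooperative before the mask. The documents do not give it, so 30%, 50% and 70% are assumptions. If no child's status changes, 300 × p occasions are classed as anxiolysis. With an assumed 80% cooperative under the gas, the net change is 80% − p, however many initially cooperative children worsened.

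| p (assumed) | Classed as anxiolysis if nothing changes | Net change if 80% are cooperative under the gas |
|---|---|---|
| 30% | 90 | +50 points |
| 50% | 150 | +30 points |
| 70% | 210 | +10 points |

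Without a reading before the mask, the three rows cannot be told apart.

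**4. What a paired reading would give.** Let b be the number who became cooperative and c the number who became uncooperative. The net change is (b − c)/n, with SE = sqrt((b + c) − (b − c)²/n)/n (Wald). Take p = 50%, so that 150 children start cooperative and 150 do not, and 240 cooperative under the gas.

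- No worsening: b = 90, c = 0. SE = sqrt(90 − 8100/300)/300 = sqrt(63)/300. Net change 30 points, 95% CI 24.8 to 35.2.
- 20% of the 150 worsen: c = 30, b = 120. SE = sqrt(150 − 8100/300)/300 = sqrt(123)/300. Net change 30 points, 95% CI 22.8 to 37.2.

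The share becoming cooperative among the initially uncooperative does depend on worsening. It is 90/150 = 60%, 105/150 = 70% or 120/150 = 80% if 0%, 10% or 20% worsen. The full table is therefore needed, not that share alone.

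**5. What estimation would give.** The 95% half-width for a single proportion, 1.96 × sqrt(p(1 − p)/300), is 5.7 points at p = 0.5, 5.2 at 0.7, 4.5 at 0.8 and 3.4 at 0.9.

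All intervals treat the 300 occasions as independent. Section 4.4 counts occasions, not children, and repeat occasions in one child could make the true intervals wider.

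**The case against.** The best defence is that section 5.1.2 sets a target state for each occasion: no or mild pain, a named sedation score, orders carried out. Efficacy in section 2.1 and the predictions in section 2.2 could then mean only that these states are reached, which one cohort can estimate. The study is openly observational, and confidence intervals are commonly left to an analysis plan. This reading is possible and shows that the study is useful as description. It does not rescue the words relief and anxiolysis, which claim a change due to the gas. The objectives and hypotheses are fixed in the protocol, not in an analysis plan.

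Second, the missing baseline rests on silence. The burden paragraph is not a visit schedule, and the data-collection forms are not shown. That stands: a pre-gas reading is not ruled out. But none is specified, and the protocol does state a reading before the gas for the vital signs.

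Third, a paired reading would still be uncontrolled, so it would not prove the second hypothesis. That also stands, which is why the rewording is needed as well. The reading's purpose is narrower: to separate children who changed from those who did not.

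Finally, the figures rest on assumed shares and concern a secondary endpoint. They show how far the reading of one result can vary and predict nothing. For pain, the primary endpoint, the remedy is rewording only. Procedural pain does not exist before the procedure, so a score before the mask would not stand in for a comparator.

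**Conclusion.** The concern holds and should be fixed. The data can describe pain, sedation and cooperation under the gas; they cannot support the conclusion that the gas achieved pain relief or anxiolysis, and more occasions would not change that. The anxiolysis definition, as written, credits the gas with cooperation that may have been there already. Across the assumed starting shares of 30% to 70%, 90 to 210 of 300 occasions would be classed as anxiolysis with no change in any child, and an 80% result would correspond to a net gain of anywhere from 50 to 10 points. The true starting share is unknown. The finding about the wording depends on none of these assumptions. The descriptive value of the study is not in question.

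**What to change.** 1. Reword sections 2.1 and 2.2 as estimation, in line with the Summary's objective: the proportions of occasions with no or mild pain, at the desired sedation level, and cooperative, each with a 95% confidence interval. State that no causal efficacy claim will be made.
2. Record the same cooperability item once before the mask. Report the full paired table (became cooperative, stayed cooperative, became uncooperative, stayed uncooperative) and the net change with its 95% confidence interval, described as uncontrolled change. Give the share becoming cooperative among the initially uncooperative only as a supplement, because it ignores worsening and is open to regression to the mean.
3. Minor and separate: children are eligible from 1 year (section 4.2), yet the item has only two states. Add a not-assessable code for those too young to follow orders.

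The cost is protocol wording and one extra tick-box per occasion. The downsides are a more modest claim and a paired change that remains uncontrolled: the procedure falls between the two readings, and reassurance or settling cannot be separated from the gas.

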3. STUDY DESIGN

Prospective, single center observational study of a random-sample cohort of pediatric patients undergoing any in-hospital minor invasive procedure during a continuous 24 months period of recruitment starting October 2024.

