4. STUDY POPULATION

4.1. Population (base)

Pediatric patients undergoing in hospital minor invasive procedures.

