9.2. Recruitment and consent

The investigator will enroll patients in the study. Informed consent by the patient and/or parents will be obtained by the investigator.

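### The random-sample label has no described sampling behind it, and 300 occasions improve precision but cannot make the conclusions unbiased

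*Protocol*

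**What the plan says.** Four places in the protocol bear on who enters the study.

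- **Section 3** gives the design as an "observational study of a random-sample cohort of pediatric patients" who have any minor invasive procedure in the hospital, recruited "during a continuous 24 months period of recruitment starting October 2024".
- **Section 4.4** cites published work for the statement that the "estimated number of patients required to evaluate analgetic and anxiolytic effect as well as safety profile is between 32 and 90", and then sets the target: "We aim to observe 300 occasions that required oxygen: nitrogen 50%:50% gas mixture in order to draw unbiased conclusions".
- **Section 9.2** is the only text on recruitment: "The investigator will enroll patients in the study". The investigator also obtains consent.
- **The source population** appears in the Summary as children "admitted to department of anesthesiology and intensive care therapy" and in Section 4.1 as "Pediatric patients undergoing in hospital minor invasive procedures". Section 3 uses the wider wording given above, and Section 4.4 counts occasions on which the gas was needed.

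Section 5.1 makes pain intensity the primary endpoint and lists no or mild pain on age-specific scales as the first outcome measure. No comparison group is described.

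**The concern.** A random sample needs a list or stream of eligible units and a chance mechanism that selects from it. The protocol claims the property in Section 3 and describes neither part. How patients are sampled, and from where, belongs in the protocol of an observational cohort, so a separate analysis plan would not be the usual place to repair this.

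The Section 4.4 sentence is a separate error. It offers the number of occasions as the reason the conclusions will be unbiased. Sample size governs random error; how units come into the sample governs selection bias.

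With no comparator, the primary result is a description of pain in whoever is enrolled. If enrolment is related to how much pain or distress a child has, the description is distorted, and a reader told that the sample is random and the conclusions unbiased has no reason to look for this. The objectives in Section 2.1 speak of children who need these procedures in general, whereas the counted units are gas occasions, so the step from one group to the other also needs care.

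**Working it through.** **1. The plan's own figure.** The target of 300 cannot be reproduced. Section 4.4 gives no expected rate, standard deviation, effect size, power or precision goal. The number itself is not disputed here, only the reason given for it.

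**2. What the number does.** For a proportion p from n independent occasions, the 95% half-width is 1.96 × √(p(1 − p)/n). The values of n are those in Section 4.4; p = 0.5 is the least favourable case.

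- n = 32: 1.96 × √(0.25/32) = 17.3 points
- n = 90: 1.96 × √(0.25/90) = 10.3 points
- n = 300: 1.96 × √(0.25/300) = 5.7 points

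These figures assume independence. Section 4.4 counts patients for the 32 to 90 and occasions for the 300. If a child contributes several correlated occasions, 5.7 is too small.

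**3. What the number does not do.** Let P be the true proportion with no or mild pain among eligible occasions. Let k be the chance of enrolment for an occasion with no or mild pain divided by the chance for one with worse pain. The observed proportion then centres on

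O = Pk / (Pk + 1 − P),

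which does not contain n. The documents give neither P nor k, so both are assumptions for illustration.

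- P = 0.70, k = 1.5: O = 1.05/1.35 = 0.778, bias +7.8 points
- P = 0.70, k = 0.67: O = 0.469/0.769 = 0.610, bias −9.0 points
- P = 0.70, k = 1: O = 0.70, bias zero
- Over P = 0.6 to 0.8 and k = 0.5 to 2, the bias runs from −17.1 points (P = 0.6, k = 0.5) to +15.0 points (P = 0.6, k = 2)

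The probability that the 95% interval covers the true P, by normal approximation, with P = 0.70:

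| k | n = 32 | n = 90 | n = 300 |
|---|---|---|---|
| 1 | 0.95 | 0.95 | 0.95 |
| 1.5 | 0.82 | 0.57 | 0.10 |
| 0.67 | 0.82 | 0.58 | 0.11 |

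For k = 1.5 and n = 300, the standard error is √(0.778 × 0.222/300) = 0.024 and the half-width is 0.047. The interval covers 0.70 only if its lower limit falls below 0.70, which has probability Φ((0.70 + 0.047 − 0.778)/0.024) ≈ Φ(−1.28) = 0.10. If enrolment is unequal, more occasions give a tighter interval around the wrong value. If it is equal, there is no bias at any n.

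**4. The source population, side by side.**

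| Place | Population |
|---|---|
| Summary | admissions to one department |
| Section 3 | any minor invasive procedure in the hospital |
| Section 4.1 | minor invasive procedures in hospital, no department named |
| Section 4.4 | occasions on which the gas was needed |

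No single frame is fixed, so no random draw from it could be specified as the text stands.

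**The case against.** The strongest reply is that the protocol does not describe a bad sampling method; it describes none. Section 9.2 says who enrols, not how cases are chosen. A reader might infer that investigators pick suitable children, but consecutive enrolment is neither stated nor excluded. That reply stands against the inference. It does not rescue the random-sample label, which still has nothing behind it.

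A reader might also infer that the pain result will look too favourable because calm children are easier to enrol. The documents do not support a direction. Entry through occasions that needed the gas could equally bring in more distressed children and lower the proportion with no or mild pain.

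Nor is restriction to gas occasions a bias in itself. The hypotheses in Section 2.2 concern application of the gas, and for children who receive it these occasions are the right population. The difficulty arises only when results are carried over to all children having these procedures, as the wording of Sections 2.1, 3 and 4.1 invites.

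Finally, one might suspect that refused or abandoned applications vanish from the 300. Nothing says so. Section 5.1 records refusal to follow instructions as part of the anxiolysis outcome, and the analysis set may be defined in an analysis plan that is not at hand. Counting a child who was only offered the gas as a pain failure would change the question and is not proposed.

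On the differing populations, the Summary can be read as naming the department where these patients are treated. That makes it a matter of alignment, but the four texts still do not agree.

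**Conclusion.** The point holds in a limited form. Two stated properties lack support: random sampling, for which no frame or draw is described, and unbiased conclusions, which do not follow from observing 300 occasions. What 300 does provide is precision, about ±5.7 points at a proportion of 0.5 if the occasions are independent. The source population needs one definition.

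Selection bias in the no-or-mild-pain result cannot be excluded, and its size and direction are unknown. The range of about −17 to +15 points rests wholly on assumed values of P and k and shows only that a bias larger than the half-width is possible. It would be wrong to conclude that the result is biased, that the bias is favourable, or that investigators select patients. The matter should be corrected while recruitment is open, because non-enrolment that is not recorded cannot be reliably reconstructed later.

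**What to change.** - **Section 3:** replace the random-sample wording with 'consecutive cohort' and enrol every eligible occasion. If that is not feasible, call it a convenience sample.
- **Summary, Sections 3 and 4.1:** name one source population and use it in all three places.
- **Log:** keep one line for each eligible occasion not enrolled (age, procedure, reason).
- **Denominator:** keep every occasion on which the gas was started, including abandoned applications. Report mask refusals before the start separately.
- **Section 4.4:** replace the closing clause about unbiased conclusions with a precision statement, for example that 300 independent occasions give a 95% half-width of about 5.7 points at a proportion of 0.5.
- **Conclusions:** limit them to children who receive the gas.

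The cost is some protocol wording, a short screening log and a more modest stated claim. The target of 300 need not change.
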